9.7. Data management

De-identified Optum EHR data will be analyzed using the Aetion Evidence Platform (AEP). Data to be used for the proposed analysis have already been linked and uploaded into the AEP. The AEP is a data-handling technology, which allows for the analysis of large patient datasets by indexing patient data into a form that can be queried by an internal patient variable language and has been previously used.^{3,4,5} Data are minimally transformed at the point of connection to the AEP, thus the original format of the raw Optum EHR data is preserved. At the point of data connection to the platform some discard rules are applied. Patient events are excluded if patient identification (ID) is missing and if the "start of enrollment" date is preceded by the "end of enrollment" date in the original data. Additionally, patient events are excluded if there are no dates associated with them, or if the start date of the event is preceded by the end date of the event (e.g. discharge date precedes admission date for an inpatient event). Action IDs are assigned to Optum EHR patient IDs and a crosswalk file is kept as a protected file available upon request to authorized parties. The data are at the individual patient level and will be analyzed within the AEP.

9.8. **Data analysis**

090177e1996138d1\Approved\Approved On: 23-Feb-2022 16:44 (GMT)

All statistical analysis will be performed in the two cohorts of interest, ie, infants aged 1 month to < 1 year and patients aged 1 to < 2 years, separately using the AEP version 4.2. Analysis combining the two cohorts of interest will not be performed.

Descriptive statistics will be presented for key variables of interest i.e., demographic characteristics, comorbidities and duration and dose of IV pantoprazole, listed in Section 9.4.3 to characterize the overall cohort treated with IV pantoprazole and in the 3 subgroups defined based on the presence or absence of GERD and EE and listed under Section 9.3.3. These will include counts and percentages for categorical data and statistics such as mean, median, standard deviation, and range for continuous variables.

For analyses of estimation of incidence rates of the outcomes of interest during follow-up, each analysis will be restricted to patients without a history of outcome of interest prior to the index date (ie baseline period); thus, for each analysis of a given specified outcome, a distinct sub-cohort will be used (i.e. for the estimation of the incidence of hepatitis, only patients with prevalent cases of hepatitis in the baseline period will be excluded from follow-up and will not contribute to person-time at risk).

For each outcome of interest, patients will be followed from the index date to whichever of the following occurs first (follow-up period):

- Occurrence of an outcome of interest,
- 90 days following the discontinuation of IV pantoprazole administration,
- Initiation of a separate IV pantoprazole infusion within 90 days following the discontinuation of IV pantoprazole administration, where a separate infusion is defined as the subsequent administration at least 7 days from the end of the previous infusion,
- Death,
- End of enrollment in the database,
- End of study period (ie, 31 December 2020).

Incidence rates of each prespecified outcome of interest will be estimated as the number of patients with a specific outcome of interest during the follow-up period divided by the total person-time at risk and reported as incidence per 1,000 person-years with associated 95% CIs, assuming a Poisson distribution. Exact Poisson confidence limits for the estimated rate are found as the Poisson means, for distributions with the observed number of events and probabilities relevant to the chosen confidence level, divided by time at risk.

$$egin{aligned} Y_l &= rac{\chi^2_{2Y,\;lpha/2}}{2} \ Y_u &= rac{\chi^2_{2(Y+1),\;1-lpha/2}}{2} \end{aligned}$$

- where Y is the observed number of events, Yl and Yu are lower and upper confidence limits for Y respectively, $\chi 2\nu$, a is the chi-square quantile for upper tail probability on ν degrees of freedom.

For the analysis of the primary objective, incidence rates for all outcomes of interest will be estimated in the overall cohort and in the 2 subgroups, i.e., patients with GERD and EE and patients with GERD, but without EE. Within the overall cohort and in the 2 subgroups, incidence rates will be calculated by duration of IV pantoprazole treatment (<4 days, ≥ 4 days). For the analysis of the secondary objective 1, incidence rates will be estimated for the subgroup of patients treated with IV pantoprazole without a diagnosis of GERD or EE in each cohort and by duration of IV pantoprazole treatment (<4 days, ≥ 4 days) within each cohort. For the analysis of the secondary objective 2, counts of the 25 most common diagnostic codes occurring within 30 days prior to starting or on the date of start of IV pantoprazole (ie, index date) through 90 days of discontinuation with IV pantoprazole in the subsets of patients with a diagnosis of GERD with or without EE will be generated. For each patient, reoccurring codes within 30 days prior to starting or on the date of start of IV pantoprazole (ie, index date) and through 90 days of discontinuation with IV pantoprazole will be counted once.

Detailed methodology for summary and statistical analyses of data collected in this study will be documented in a statistical analysis plan (SAP), which will be dated, filed and maintained

by the sponsor. The SAP may modify the plans outlined in the protocol; any major modifications of primary endpoint definitions or their analyses would be reflected in a protocol amendment.

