9. RESEARCH METHODS

9.1. Study design

This will be a retrospective cohort study with no comparator group. No a priori hypotheses are specified. Descriptive analyses including an estimation of incidence rates will be performed.

9.2. **Setting**

The study will be conducted using Optum's longitudinal integrated EHR from the US¹, which is described in Section 9.5 This data source includes data from adjudicated administrative insurance claims, inpatient electronic health records, as well as outpatient EHR enabling capture of exposure to IV pantoprazole in the study population of interest. The study period will be defined from 01 January 2007 to 31 December 2020.

9.3. **Study population**

Two separate cohorts, ie, infants aged 1 month to <1 year and patients aged 1 to <2 years will be identified during the study period using the following inclusion and exclusion criteria.

9.3.1. **Inclusion criteria**

Patients must meet all of the following inclusion criteria to be eligible for inclusion in the study:

- 1. At least one administration of IV pantoprazole during the study period from January 1, 2007 to December 31, 2020, and
- 2. For the cohort of infants aged 1 month to <1 year (Cohort 1): Age 1 month to <1 year on the index date (ie, the date of first administration of IV pantoprazole); For the cohort of patients aged 1 to <2 years (Cohort 2): Age 1 to <2 years on the index date.
- 3. Patients must be enrolled in the database for at least 30 days prior to the index date

In addition to this 30-day lookback window, patients will be further excluded based on the occurrence of a history of outcomes of interest identified in Table 3 occurring prior to the index date.

9.3.2. **Exclusion criteria**

Patients meeting any of the following criteria will not be included in the study:

1. Patients with any of the following ICD-9-CM or ICD-10-CM codes occurring prior to or on the index date indicating a preterm birth or birth weight less than 2.36 kilograms will be excluded:

ICD-9-CM codes: 765.01-765.08; 765.10-765.19; 765.21-765.28

ICD-10-CM codes: P07.21-P07.26; P030-P039; P07.01-P07.03; P07.14-P07.18

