9.4. Variables

9.4.1. Exposure ascertainment

Exposure to IV pantoprazole will be identified from inpatient procedure and drug codes including any of the following NDC and HCPCS codes shown in Table 2. Only the first treatment episode during the study period will be of interest.

Version 2.0, 10 February 2022

Table 2. NDC and HCPCS Codes indicating IV administration of pantoprazole			
Code	Description		
NDC			
0008-0941-01	40 mg/vial pantoprazole		
0008-0941-02	40 mg/vial pantoprazole (10 vials)		
0008-0941-03	40 mg/vial pantoprazole (25 vials)		
0008-2001-01	40 mg/vial pantoprazole Single vial		
0008-2001-10	40 mg/vial pantoprazole 10 vials		
0008-2001-25	40 mg/vial pantoprazole 25 vials		
0008-4001-01	40 mg/vial pantoprazole Single vial		
0008-4001-10	40 mg/vial pantoprazole 10 vials		
0008-4001-25	40 mg/vial pantoprazole 25 vials		
0008-0923-51	40 mg/vial pantoprazole Single vial		
0008-0923-55	40 mg/vial pantoprazole 10 vials		
0008-0923-60	40 mg/vial pantoprazole 25 vials)		
HCPCS			
S0164	Injection pantoprazole sodium, 40 mg		
C9113	Injection, pantoprazole sodium, per vial		

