9.4.2. Outcomes of interest

The outcomes of interest are listed in Table 3 below. These outcomes were based on the Investigator's Brochure (version 4.0 June 2021) and expert clinical judgment. The first occurrence of each outcome is defined based on the presence of at least one ICD-9-CM or ICD-10-CM diagnosis code identified in the inpatient or outpatient setting during the follow-up period.

Outcome of interest	Operationalization: ICD-10-CM code	Operationalization: ICD-9-CM code
Agranulocytosis	D70.2 Other drug-induced agranulocytosis D70.1 Agranulocytosis secondary to cancer chemotherapy	288.03 Drug induced neutropenia
Thrombocytopenia	D69.3 Immune thrombocytopenic purpura D69.59 Other secondary thrombocytopenia D69.6 Thrombocytopenia, unspecified D69.41 Evans syndrome D69.49 Other primary thrombocytopenia	287.31 Immune thrombocytopenic purpura 287.49 Other secondary thrombocytopenia 287.5 Thrombocytopenia, unspecified 287.30 Primary thrombocytopenia, unspecified 287.32 Evans syndrome 287.39 Other primary thrombocytopenia
Leukopenia	D72.810 Lymphocytopenia D72.818 Other decreased white blood cell count D72.819 Decreased white blood cell count, unspecified D70.8 Other neutropenia D70.9 Neutropenia, unspecified D70.0 Congenital agranulocytosis	288.51 Lymphocytopenia 288.59 Other decreased white blood cell count 288.50 Leukocytopenia, unspecified 288.09 Other neutropenia 288.00 Neutropenia, unspecified
Pancytopenia	D61.811 Other drug-induced pancytopenia	284.12 Other drug-induced pancytopenia
	D61.818 Other pancytopenia	284.19 Other pancytopenia

Hypersensitivity (including anaphylactic reactions and anaphylactic shock)	K52.2x Allergic and dietetic gastroenteritis and colitis M31.0 Hypersensitivity angiitis T78.2x Anaphylactic shock, unspecified T78.4x Other and unspecified allergy M36.4x Arthropathy in hypersensitivity reactions classified elsewhere	558.3 Allergic gastroenteritis and colitis 446.20 Hypersensitivity angiitis, unspecified 446.21 Goodpasture's syndrome 446.29 Other specified hypersensitivity angiitis 995.0 Other anaphylactic reaction, Not elsewhere classified (NEC) 995.3 Allergy, unspecified, NEC 713.6 Arthropathy associated with hypersensitivity reaction
Hyperlipidemia	E78.49 Other hyperlipidemia E78.5 Hyperlipidemia, unspecified	272.4 Other and unspecified hyperlipidemia
Hypertriglyceride mia	E78.1 Pure hyperglyceridemia	272.1 Pure hyperglyceridemia

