9.9. Quality control

Aetion will build measures for cohort inclusion, outcomes and covariates based on codes and algorithms described in this protocol, which were collaboratively agreed upon with Pfizer. All measures created, cohorts developed, statistical analyses implemented, and tables completed will undergo quality control review by at least one additional analyst or scientist under the supervision of the Science Lead. All analyses will separately be doubly implemented by an independent team. Results of single and double implementations will be compared, and any discrepancies will be adjudicated by a third-party senior science team

member not involved in either implementation. Furthermore, the Science Lead will review all results tables to confirm accuracy, logical flow, and appropriate format. This protocol will be strictly followed when conducting the analysis of this study.

The data were subject to quality control procedures. The data provider was contacted to help rectify any problems identified during the quality control procedures, including if the files received appeared to be incomplete or the data values were implausible. The data are loaded into the Aetion Evidence Platform after minimal processing into patient longitudinal timelines to enable representation of the original data and without any data loss. Events are required to have a valid start date. Record counts are cross-checked for validation and compared to the original data counts.

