9.10. Strengths and limitations of the research methods

This study has several strengths. It is a population-based study, and while the use of IV pantoprazole in infants aged 1 month to <1 year and patients aged 1 to <2 years is rare, this database includes a relatively large number of IV pantoprazole users in these age groups, facilitating generation of precise incidence rates. Given the age of the study population, it is less likely that patients will seek health care outside of the Optum EHR system during the baseline period, and therefore, it is less likely that an outcome of interest occurring during the baseline period will be missed; thus prevalent conditions are unlikely to be mistaken for incident events. Similarly, given the relatively short follow up time, it is less likely that patients will seek care outside of the Optum EHR system during this period, and therefore, that incidence events will be missed.

The study also has several limitations. As is the case in any administrative claims-based study without outcome validation/adjudication, outcome misclassification is a possibility. Diagnosis codes may be incorrect, or may be included as part of the diagnostic rule-out process rather than an indication of diagnosis itself. Conditions not requiring treatment or office visits tend to be systematically undercoded in such databases. It is possible that this study will only capture severe manifestations of such disorders. However, this limitation is likely to be applicable to two outcomes of interest -vomiting and diarrhea as patients experiencing these symptoms may not always visit a physician for care. Another well-recognized limitation of claims database analysis is that the gap between disease onset and date of diagnosis. However, in an incidence analysis, the time at risk begins on the date of IV pantoprazole administration (ie index date), not at disease onset. For outcome events, as only the incidence of new events is considered that occur after the initiation of IV pantoprazole, the impact of this limitation is expected to be minimal, as complications arising in infants would almost certainly be captured in the inpatient setting. Additionally, this would result in underestimating the incidence rate as time at risk would be inflated.

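### Outcomes are classed as history or incident by code date alone, around an index date usually inside a hospital stay, and the protocol does not say which date an inpatient diagnosis carries

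*Protocol*

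**What the plan says.** **Index date and exposure.** The index date is "the date of first administration of IV pantoprazole" (section 9.3.1). Section 9.4.1 states: "Exposure to IV pantoprazole will be identified from inpatient procedure and drug codes".

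**History.** In section 9.8, "each analysis will be restricted to patients without a history of outcome of interest prior to the index date (ie baseline period". Section 9.3.1 likewise excludes on outcomes that occurred before the index date.

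**Incident event.** Also in section 9.8, "patients will be followed from the index date to whichever of the following occurs first". Under section 9.4.2 an outcome is "at least one ICD-9-CM or ICD-10-CM diagnosis code identified in the inpatient or outpatient setting during the follow-up period". Section 9.10 confirms that only diagnosis codes are used, without procedure or treatment codes.

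**Dates.** Section 9.7 discards events whose start and end dates are in the wrong order and gives as its example "discharge date precedes admission date for an inpatient event". Section 9.9 adds: "Events are required to have a valid start date". Neither section says which date a diagnosis recorded during a stay receives.

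**Reassurance.** Section 9.10 holds that prevalent conditions are unlikely to be taken for incident ones, because children this young seldom seek care outside the system. It calls the effect of the gap between onset and diagnosis minimal because "complications arising in infants would almost certainly be captured in the inpatient setting".

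**The concern.** A date-only rule separates prior conditions from new ones only if the code date is close to onset, at least on the scale of days that matters here. Around an index date inside a hospital stay, that cannot be taken for granted. A diagnosis made during the stay might be stored under the admission date, the discharge date or its own entry date, and the same clinical event can change class accordingly.

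The index stay is when the child is receiving the drug. Several listed outcomes (low blood counts, electrolyte disturbances, liver injury, infusion-site complications) could plausibly arise either on treatment or from the illness that led to admission. The study has no comparator, and its primary result is the absolute rate in each cohort, so no contrast exists in which such an error might cancel.

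The argument in section 9.10 is about capture: whether the event is recorded in the system at all. It does not deal with whether the event came before or after the first dose. If most events are recorded in hospital, as that section expects, most are recorded where ordering is hardest.

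**Working it through.** **1. What the date logic does.** Take a child admitted before the day of the first dose, with an outcome coded only on that stay.

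| Date carried by the code | Event arose on treatment | Condition present on admission |
|---|---|---|
| Admission date | Before index: child removed, event lost | Before index: removed, correct |
| Discharge or other late date | After index: counted, correct | After index: counted as incident, wrong |
| Diagnosis-level date close to onset or recognition | Usually correct | Usually correct |

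For one code under one dating rule only one of the two errors can occur. They act in opposite directions. The first also needs treatment to begin after the day of admission.

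**2. The plan's own figure.** Table 5 gives 75 events in 7,489 infants with 95% limits 0.0080 to 0.0125. With p = 75/7,489 = 0.01001 and z = 1.96, the Wilson centre is (p + z²/2n)/(1 + z²/n) = 0.01027. The half-width is z√(p(1−p)/n + z²/4n²)/(1 + z²/n) = 0.00227. The limits are 0.0080 and 0.0125, as printed. All twelve rows of Table 5 reproduce from the rounded event counts. Nothing in that table is in dispute; it measures sampling error only.

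**3. Illustration A (all inputs assumed).** 1,000 children start treatment the day after admission and each is followed for 94 days (4 treatment days plus 90). 5% have the condition on admission, first coded on that stay. 1% develop it in the stay after starting. Every in-stay code takes the same type of date.

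- True rate: 10/(950 × 94/365.25) × 1,000 = 40.9 per 1,000 person-years.
- Admission-dated: 0 in-stay events; 10 + 50 = 60 children removed as history.
- Discharge-dated: 60/(1,000 × 94/365.25) × 1,000 = 233.1; ratio 233.1/40.9 = 5.7.
- With 2% on admission: 30/(1,000 × 94/365.25) × 1,000 = 116.6, against 10/(980 × 94/365.25) × 1,000 = 39.6; ratio 2.9.

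**4. Illustration B (cohort 1 size, other inputs assumed).** 7,489 × 94/365.25 = 1,927 person-years, kept fixed for simplicity. Take 75 true events, or 75/1,927 × 1,000 = 38.9. The exact Poisson limits in the chi-square form of section 9.8 are 30.6 to 48.8.

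| Assumption | Events | Rate per 1,000 person-years |
|---|---|---|
| 25% of true events removed as history | 56 | 29.1 |
| 50% removed | 38 | 19.7 |
| 75% removed | 19 | 9.9 |
| 0.2% with the condition on admission, counted as incident | 75 + 15 = 90 | 46.7 |
| 0.5% | 75 + 37 = 112 | 58.1 |
| 1% | 75 + 75 = 150 | 77.8 |
| 2% | 75 + 150 = 225 | 116.7 |
| 5% | 75 + 374 = 449 | 233.0 |

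All but the 0.2% row lie outside 30.6 to 48.8. Misdating of moderate extent would therefore not be covered by the planned interval. The documents do not show whether it occurs to that extent.

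**5. What the plan does to test it.** Table 6 has two sensitivity analyses, on the 30-day enrollment requirement and on ICD version. Neither varies how index-stay codes are ordered.

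**The case against.** The strongest reply is that a reader might infer from section 9.7 that inpatient diagnoses are held by admission and discharge date, and so that the bias is present and large. The documents do not support that. The admission and discharge wording is one example in a discard rule and describes a stay-type record, not the date on a diagnosis code. Section 9.7 also says the raw format of the data is preserved, and section 9.5 lists coded diagnoses and administered medications among the data elements. If diagnoses carry their own dates, both errors shrink or disappear. This part of the reply stands.

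Three further points stand in part.

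- Section 9.4.1 does not say that exposure is found *only* in inpatient codes, and section 9.2 counts outpatient records among the sources that enable exposure capture. A usual index date inside a stay remains the natural reading, but the share of index dates after the admission day is not given.
- The choice of date field is often left to the SAP, and section 9.8 defers detailed methods to it. However, the protocol itself fixes the history rule and the outcome definition, and it asserts that confusion of prevalent with incident conditions is unlikely. Section 9.9 says the protocol will be strictly followed.
- Section 9.10 concedes outcome misclassification and possible overestimation from code-only algorithms. That concerns whether a code is true, not whether it came before or after the first dose. The same section says the onset-to-diagnosis gap would lead to underestimation; late dating of admission conditions would do the reverse.

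**Conclusion.** The point holds in conditional form. The protocol relies on code date alone to separate on-treatment events from conditions present on admission. It places the cut-off where that separation is fragile and does not establish that inpatient codes carry a date able to support it. The reassurance in section 9.10 answers a different question.

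No size or sign of bias can be derived. The documents give no share of treatment starts after the admission day, no prevalence of the outcomes on admission and no dating rule. The 5.7-fold and 2.9-fold ratios, the total loss of in-stay events and the cohort 1 figures are illustrations under assumed inputs; the ratios largely reflect the assumed split between admission and on-treatment conditions. They show that the error could exceed sampling error, not that it does. This should be fixed because the absolute rate is the primary result and the remedy needs no new data collection.

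**What to change.** - **Section 9.8:** state which date an inpatient diagnosis takes. Prefer a diagnosis-level date; failing that, use a present-on-admission indicator if the data hold one (present = history, not present = incident). The documents mention no such indicator, so its availability must be checked.
- **Table 6:** add a sensitivity analysis, at least for the overall cohort and the two GERD subgroups, that classes index-stay codes that cannot be ordered first all as history and then all as incident. Report separately the rate of events first coded after discharge from the index stay.
- **Section 9.10:** qualify the statements on prevalent conditions and minimal impact, and refer to these results.

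The cost is extra programming and tables, and wide bounds for some outcomes. Applied everywhere, the exercise would cover 25 outcomes × 2 cohorts × 4 populations (overall plus 3 subgroups) × 3 duration groupings (all, under 4 days, 4 days or more) = 600 rates. Limited to the overall cohort and the two GERD subgroups without the duration split, it is 25 × 2 × 3 = 150 rates, each with two bounds and a post-discharge rate.

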K74.00 Hepatic fibrosis, unspecified K74.01 Hepatic fibrosis, early fibrosis K74.02 Hepatic fibrosis, advanced fibrosis K74.1 Hepatic sclerosis K74.3 Primary biliary cirrhosis K74.4 Secondary biliary cirrhosis K74.5 Biliary cirrhosis, unspecified K74.60 Unspecified cirrhosis of liver K74.69 Other cirrhosis of liver K75x Other inflammatory liver diseases K75.2 Nonspecific reactive hepatitis K75.3 Granulomatous hepatitis, not elsewhere classified K75.4 Autoimmune hepatitis K75.81 Nonalcoholic steatohepatitis (NASH) K75.89 Other specified inflammatory liver diseases K75.9 Inflammatory liver disease, unspecified K76x Other diseases of the liver K76.0 Fatty (change of) liver, not elsewhere classified K76.1 Chronic passive congestion of liver K76.2 Central hemorrhagic necrosis of liver K76.3 Infarction of liver K76.4 Peliosis hepatis K76.5 Hepatic venoocclusive disease

	10 1 cordary 2022	
	K76.6 Portal hypertension K76.7 Hepatorenal syndrome K76.81 Hepatopulmonary syndrome K76.89 Other specified diseases of liver K76.9 Liver disease, unspecified K77 Liver disorders in diseases classified elsewhere K71.6 Toxic liver disease with hepatitis, not elsewhere classified K71.2 Toxic liver disease with acute hepatitis K71.3 Toxic liver disease with chronic persistent hepatitis K71.4 Toxic liver disease with chronic lobular hepatitis K71.50 Toxic liver disease with chronic active hepatitis without ascites K71.51 Toxic liver disease with chronic active hepatitis with ascites R17 Unspecified jaundice	
Urticaria	L50.0 Allergic urticaria L50.1 Idiopathic urticaria L50.8 Other urticaria L50.9 Urticaria, unspecified	708.0 Allergic urticaria 708.1 Idiopathic urticaria 708.8 Other specified urticaria 708.9 Urticaria, unspecified
Angioedema	T78.3XXA Angioneurotic edema initial encounter T78.3XXD Angioneurotic edema subsequent encounter T78.3XXS Angioneurotic edema sequela	995.1 Angioneurotic edema, not elsewhere classified

10 February 2022

2.0,

Version

version 2.0, 101	editiary 2022	Ī
Stevens- Johnson syndrome	L51.1 Stevens-Johnson syndrome L51.3 Stevens-Johnson syndrome -toxic epidermal necrolysis overlap syndrome	695.13 Stevens-Johnson syndrome 695.14 Stevens-Johnson syndrome- toxic epidermal necrolysis overlap syndrome
Lyell syndrome	L51.2 Toxic epidermal necrolysis [Lyell]	695.15 Toxic epidermal necrolysis

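### Pancytopenia before the index date is not treated as history for thrombocytopenia or leukopenia, so a prevalent cytopenia can be counted as incident

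*Protocol*

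**What the plan says.** **History rule.** Protocol Section 9.8 restricts each incidence analysis to children without a history of the outcome concerned: "thus, for each analysis of a given specified outcome, a distinct sub-cohort will be used". The illustration that follows is explicit about how narrow this is: "only patients with prevalent cases of hepatitis in the baseline period will be excluded from follow-up". Hepatitis has since been merged into hepatobiliary injury, but the example still shows a per-outcome rule.

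**Event rule.** Section 9.4.2 states: "The first occurrence of each outcome is defined based on the presence of at least one ICD-9-CM or ICD-10-CM diagnosis code". The codes are those in the outcome's own row of Table 3.

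**Code lists.** The pancytopenia row contains D61.811 and "D61.818 Other pancytopenia", with ICD-9-CM 284.12 and 284.19. The thrombocytopenia row, for example "D69.6 Thrombocytopenia, unspecified", and the leukopenia row contain none of these four codes. No text links the rows.

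**A broader wording elsewhere.** Section 9.3.1 says that "patients will be further excluded based on the occurrence of a history of outcomes of interest identified in Table 3", without limiting this to the outcome under analysis.

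**The concern.** The incidence analyses are meant to count new events only. Section 9.10 lists as a strength that prevalent conditions are unlikely to be taken for incident ones, and bases this on children being unlikely to seek care outside the database. Complete capture does not help here. The prior pancytopenia code may be fully recorded, yet the rule does not look at it when it assembles the thrombocytopenia and leukopenia cohorts.

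At stake are two outcome rates under the primary objective, and the same two under secondary objective 1. Children with an established blood disorder are plausible candidates for repeated platelet and white-cell codes. A first such code after the index date would enter the numerator as though it had arisen after IV pantoprazole began.

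**Working it through.** **Step 1: compare the rows of Table 3.**

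| Row | ICD-10-CM | ICD-9-CM |
|---|---|---|
| Pancytopenia | D61.811, D61.818 | 284.12, 284.19 |
| Thrombocytopenia | D69.3, D69.41, D69.49, D69.59, D69.6 | 287.30, 287.31, 287.32, 287.39, 287.49, 287.5 |
| Leukopenia | D70.0, D70.8, D70.9, D72.810, D72.818, D72.819 | 288.00, 288.09, 288.50, 288.51, 288.59 |

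The pancytopenia row shares no code with either of the other two.

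**Step 2: follow a child through the rules.** Take a child with D61.818 before the index date and no code from the other two rows.
- Pancytopenia analysis: excluded by history.
- Thrombocytopenia and leukopenia analyses: no history in the row, so the child is kept and adds person-time.
- If D69.6 or D72.819 is first recorded in follow-up, it counts as incident.

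Two conditions must both hold: a component code appears after the index date, and none appeared before. If pancytopenia and its components were coded together at baseline, the child is already excluded and nothing goes wrong.

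**Step 3: the plan's own figures.** Table 5 (Section 9.6) is the only numeric precision statement. Wilson score intervals on its rounded counts reproduce all 12 intervals to four decimals; for example, 75/7,489 gives 0.0080 to 0.0125 and 67/6,657 gives 0.0079 to 0.0128. This point does not dispute them.

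**Step 4: illustrate the size.** False events = n × p × f, where
- n is the cohort size: 7,489 or 6,657 (Section 9.6);
- p is the proportion whose only relevant prior code is pancytopenia: assumed 0.1% to 1%;
- f is the proportion of those with a first platelet code in follow-up: assumed 0.5.

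Results:
- Infants: 7,489 × 0.001 × 0.5 = 3.7 (about 4); 7,489 × 0.01 × 0.5 = 37.4 (about 37).
- Ages 1 to <2 years: 6,657 × 0.001 × 0.5 = 3.3 (about 3); 6,657 × 0.01 × 0.5 = 33.3 (about 33).
- The count scales directly with f. At f = 0 it is zero. At f = 1 it doubles, to about 7 to 75 infants.

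**Step 5: put this on the rate scale.** Assume 90 days of follow-up for every infant: 7,489 × 90 / 365.25 = 1,845 person-years. Suppose thrombocytopenia is recorded in 75 infants, the 1% row of Table 5: 75 / 1,845 = 40.6 per 1,000 person-years. If 7 of those 75 had prior pancytopenia, removing them gives 68 / 1,845 = 36.8, a fall of 9%. Person-time is left unchanged for simplicity. Both the 75 and the 7 are hypothetical.

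**The case against.** **Separate rows are a legitimate choice.** The study is descriptive and has no hypotheses. Pancytopenia, thrombocytopenia and leukopenia are prespecified as separate outcomes, and nothing says that the rows are nested. This stands as far as events are concerned. A reader might infer that new pancytopenia cases are lost. They are not: a case coded only as pancytopenia is reported in its own row, and whether it should also count as a component event is a choice between two defensible conventions. The argument does not cover history, because there the stated purpose is to remove prevalent conditions.

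**The overlap code.** A reader might also infer that Stevens-Johnson/toxic epidermal necrolysis overlap drops out of the skin outcomes. It does not. "L51.3 Stevens-Johnson syndrome -toxic epidermal necrolysis overlap syndrome" is listed in the Stevens-Johnson row, with 695.14, and is counted there. It is absent only from the Lyell row ("L51.2 Toxic epidermal necrolysis [Lyell"; 695.15), which is a convention that needs at most a footnote.

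**Direction and size are unknown.** If pancytopenia-only events were also regarded as missing component events, the two effects would push the rate in opposite directions: 7 events added and 7 removed would leave the 40.6 unchanged. The documents contain no pancytopenia frequency, so no net bias can be claimed. That the upper illustration of 37 equals the event count in Table 5's 0.005 row follows from the assumed inputs and carries no information.

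**Section 9.3.1 may already close the gap.** Read literally, it would exclude a child with any prior Table 3 outcome. Section 9.8 is the more specific text and says otherwise, so the broader wording is a second thing to reconcile and does not settle the matter.

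**The limitations are disclosed.** Section 9.10 admits outcome misclassification and possible overestimation from code-only definitions. That concerns wrong or over-sensitive codes, whereas here a correctly recorded prior diagnosis is ignored by rule.

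**Conclusion.** The point holds for history. Under Section 9.8 and Table 3 as written, pancytopenia before the index date does not remove a child from the thrombocytopenia or leukopenia analysis, and a first component code in follow-up is counted as incident although the condition was prevalent. This is a gap in the outcome definitions. It is neither an arithmetic error nor evidence of a known bias.

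Its size cannot be found from the documents. On the assumptions of Step 4 it is about 4 to 37 false thrombocytopenia events among infants and about 3 to 33 in the older cohort, and it falls to zero if component codes always accompany pancytopenia before the index date. The same reasoning applies to leukopenia, with its own unknown f.

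It is not a detail left to the SAP. The code lists and the history rule are fixed in the protocol, and Section 9.9 says that measures are built from the protocol's codes and that the protocol will be strictly followed.

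**What to change.** - In Section 9.8, state that D61.811, D61.818, 284.12 or 284.19 recorded before the index date counts as history for the thrombocytopenia and leukopenia analyses. Keep the pancytopenia row as it is.
- Reword the history sentence in Section 9.3.1 so that it matches the outcome-specific rule in Section 9.8, including this addition.
- Optionally, report the two component rates a second time with new pancytopenia codes counted as events, since a pancytopenia-only case otherwise appears only in its own row.
- Optionally, add a footnote to Table 3 saying that the overlap code is counted under Stevens-Johnson syndrome only.

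The cost is a sentence and a small change to the history code list. The at-risk cohort shrinks slightly for two outcomes: with prior pancytopenia in 0.1% to 1%, by at most about 7 to 75 of 7,489 infants, before allowing for those already excluded by a component code. If the optional second rate is reported, some cases will appear in more than one row, and the table should say so.
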